5.3.3 Sensitivity Analyses for Primary Virology Endpoint

A sensitivity analysis may be performed, whereby only data obtained at the nominal timepoint is used. This means that the time windows in [Table 4](#) would not be applicable; only samples collected on the scheduled timepoints (Days 3, 5, and 7) would be included in the analysis.

At the end of the study, sensitivity analyses will also be performed for each cohort with a combined placebo group from all cohorts.

5.3.4 Supplementary Analyses for Primary Virology Endpoint

To supplement the main analysis, an exploratory time-weighted average change from baseline may also be performed. This will be calculated as the AUC of the change from baseline viral load divided by its total time interval (time of last observation minus time of first observation).

5.3.5 Subgroup Analyses for Primary Virology Endpoint

The change from baseline in the amount of SARS-CoV-2 virus RNA may be compared between the treatment groups and pooled placebo group for the following subgroups:

- Baseline viral load (for example: high, low; based on median baseline viral load)
- Baseline anti-SARS-CoV-2 antibody (spike protein) status (positive, negative)
- Time from symptom onset to treatment (≤ 3 days, > 3 days)
- Any underlying health conditions (yes, no)

Subgroup analyses will be analyzed descriptively at each timepoint and may be plotted over time.

5.4 SECONDARY ENDPOINTS ANALYSES

All secondary endpoints will be analyzed descriptively and summary statistics will be presented. Descriptive comparisons will be made for each AT-527 group and a pooled placebo group containing patients from all cohorts. For time to event endpoints, a Kaplan-Meier plot and the median time to response will be presented along with the 80% CI. For proportion, frequency and incidence endpoints, the number, proportion and difference in proportions along with 80% CIs will be presented. For area under the curve (AUC) endpoints, summary statistics will be presented.

5.4.1 Potential Further Statistical Analyses

If required, in addition to the descriptive analyses, formal statistical analysis may also be presented for secondary endpoints.

Time to event secondary virology and efficacy endpoints may be analyzed using the generalized Wilcoxon test or log-rank test (as appropriate), which may be stratified for appropriate covariates. Secondary proportion, frequency and incidence endpoints for virology and efficacy may be analyzed using the Fisher's Exact test. AUC and duration secondary endpoints may be analyzed using the Mann-Whitney U test, where AUC is calculated using the trapezoidal method.

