5.4.2.3 Secondary Endpoints (Efficacy)

Time to event and duration efficacy secondary endpoints include:

- **Time to alleviation or improvement of COVID-19 symptoms (Items 1–12 of the COVID-19 Symptom Diary) maintained for a duration of 21.5 hours**
 - Time to alleviation or improvement is defined as the length of time (hours) taken from start of treatment to the point at which all of the following three criteria are met and maintained for a concurrent duration of at least 21.5 hours:
 - Alleviation of all new COVID-19 symptoms, defined as a score of 0 [none] or 1 [mild] of the COVID-19 Symptom Diary
 - Improvement of all pre-existing symptoms that had worsened due to COVID-19, defined as at least a single category improvement from baseline on the Likert scale. For example, a symptom classed as severe at baseline must improve to moderate, mild, or none, and a symptom classed as moderate at baseline must improve to mild or none.
 - Maintain/improvement of all pre-existing symptoms that had not worsened due to COVID-19, defined as either remaining the same score or at least a single category improvement from baseline on the Likert scale.
- **Time to alleviation or improvement of COVID-19 symptoms (Items 1–12 of the COVID-19 Symptom Diary) maintained for a duration of 43 hours**
 - Time to alleviation or improvement is defined as the length of time (hours) taken from start of treatment to the point at which all of the following three criteria are met and maintained for a concurrent duration of at least 43 hours:
 - Alleviation of all new COVID-19 symptoms, defined as a score of 0 [none] or 1 [mild] of the COVID-19 Symptom Diary
 - Improvement of all pre-existing symptoms that had worsened due to COVID-19, defined as at least a single category improvement from baseline on the Likert scale. For example, a symptom classed as severe at baseline must improve to moderate, mild, or none, and a symptom classed as moderate at baseline must improve to mild or none.
 - Maintain/improvement of all pre-existing symptoms that had not worsened due to COVID-19, defined as either remaining the same score or at least a single category improvement from baseline on the Likert scale.

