The efficacy endpoint definition includes both alleviation of new COVID-19 symptoms and maintenance/improvement of pre-existing COVID-19 symptoms to allow for the possibility that some patients may have underlying health conditions with symptoms similar to those observed with COVID-19 (e.g., cough in a patient with chronic obstructive pulmonary disease). At screening, patients will be assessed with a 14-item COVID-19 symptom severity assessment to identify pre-existing symptoms (within the prior 30 days), and assess if they worsened due to COVID-19. Symptoms that are not pre-existing are considered to be new symptoms and need to achieve sustained alleviation (score of 0 or 1) to meet the endpoint, as described above.

- **Time to alleviation of COVID-19 signs and symptoms maintained for a duration of 21.5 hours**
 - Time to alleviation of COVID-19 symptoms is defined as the length of time (hours) taken from start of treatment to the point at which the following criterion is met and maintained for at least 21.5 hours: Score of 0 or 1 on Items 1–12 of the COVID-19 Symptom Diary, regardless of if the symptom is pre-existing or new.
- **Time to alleviation of COVID-19 signs and symptoms maintained for a duration of 43 hours**
 - Time to alleviation of COVID-19 symptoms is defined as the length of time (hours) taken from start of treatment to the point at which the following criterion is met and maintained for at least 43 hours: Score of 0 or 1 on Items 1–12 of the COVID-19 Symptom Diary, regardless of if the symptom is pre-existing or new.
- **Duration of fever**
 - Duration of fever is defined as the time from start of treatment to return to an afebrile state (temperature $\leq 37.5^{\circ}\text{C}$) maintained for at least 21.5 hours.
- **Time to alleviation of an individual symptom**
 - Time to alleviation of an individual symptom is defined as the length of time (hours) taken from the start of treatment to the point at which the following criterion is met and maintained (for each individual symptom) for at least 21.5 hours:
 - Score of 0 or 1 for Items 1–12 of the COVID-19 Symptom Diary
 - Score of 0 for Items 13 and 14 of the COVID-19 Symptom Diary

For each of these endpoints, the time at which the endpoint is met is the time of the start of the period when the criterion is met.

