These endpoints will be summarized using descriptive statistics by treatment group, as well as Kaplan-Meier plots where appropriate. The median time to response will be presented along with the 80% CI. For all cohorts, the efficacy time to event endpoints will be described through Day 28 between the AT-527 group and the combined placebo group from all available cohorts using the mITTi population.

A summary of the symptom severity for each symptom in the COVID-19 symptom diary will be provided at baseline, Day 14 and Day 28 for each treatment group and pooled placebo group. Day 14 (morning) assessments are to be used for the Day 14 summary. If the morning sample is missing, the evening sample will be used.

For efficacy time to event endpoints, deaths will be right censored at Day 28. Consequently, for these endpoints, participants censored on Day 28 reflect two different states, death and failure to meet the improvement outcome criterion. Therefore, it is

important to understand the outcome in the context of the number and timing of deaths by treatment group.

Intercurrent events are those that occur after treatment initiation and either preclude observation of the variable or affect its interpretation. Intercurrent events and missing data will be accounted for through censoring rules, as described in [Table 9](#) below.

Table 9 Efficacy Time to Event Censoring

Event	Censor	Date and Time
Death prior to meeting endpoint	Yes	Final timepoint on Day 28
Discontinuation or lost to follow-up up to Day 28 for any reason prior to meeting endpoint	Yes	Last observed COVID-19 symptom diary assessment
Do not meet the endpoint	Yes	Final timepoint on Day 28

Frequency efficacy endpoints include:

- **Frequency of COVID-19-related complications**
 - COVID-19-related complications include: death, hospitalization, radiologically confirmed pneumonia, acute respiratory failure, sepsis, coagulopathy, pericarditis, myocarditis, and cardiac failure.

For frequency efficacy endpoints, the number, proportion and difference in proportions between the AT-527 group and the pooled placebo group from all available cohorts, along with 80% CIs will be presented by treatment group.

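### SAP 5.4.1 names the Mann-Whitney test for duration endpoints, but the only one, duration of fever, is a time to event with censoring that this test cannot use

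*SAP*

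**What the plan says.** SAP 5.4.1 sets out formal tests that may be added, if required, to the descriptive analysis of secondary endpoints. It assigns them by type of endpoint. One sentence reads, in part, "Time to event secondary virology and efficacy endpoints may be analyzed using the generalized Wilcoxon test or log-rank test (as appropriate". A later sentence in the same paragraph reads "AUC and duration secondary endpoints may be analyzed using the Mann-Whitney U test".

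SAP 5.4.2.3 puts both types in one list, introduced by "Time to event and duration efficacy secondary endpoints include". Fever is in that list: "Duration of fever is defined as the time from start of treatment to return to an afebrile state", which must then hold for at least 21.5 hours. The list is to be summarised descriptively, "as well as Kaplan-Meier plots where appropriate".

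The section then states that "Intercurrent events and missing data will be accounted for through censoring rules", pointing to Table 9. For discontinuation or loss to follow-up before the endpoint is met, Table 9 gives the censoring time as "Last observed COVID-19 symptom diary assessment". For death, and for patients who never meet the endpoint, it gives "Final timepoint on Day 28".

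Protocol 4.5.7.2 has temperature recorded in the symptom diary, so the diary-based censoring time suits the fever endpoint.

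**The concern.** Mann-Whitney ranks one number per patient and has no way to use the information that a value is only a lower bound. For a patient who leaves the study while febrile, the only time the SAP supplies is the last diary entry, which for an early dropout is an early time. If that time is ranked as though it were the duration, an unresolved fever counts as a short one. An arm that loses more febrile patients early would then look better on fever for that reason alone. A real benefit could be hidden if the losses fell mainly on placebo.

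**Working it through.** **1. The passages side by side.** No other secondary endpoint is named as a duration, so the word in 5.4.1 can refer only to fever. Fever is defined as the time from a fixed start to an event. Its section offers censoring as the only rule for missing data. The tests in 5.4.1 that accept censored times are tied to the other label. The SAP does not say how a censored fever time would enter a Mann-Whitney test. The plan states no figure for this endpoint, so there is none to reproduce.

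**2. Rank example.** Let both arms have true durations of 24, 36, 48, 72 and 96 h. U counts the active-placebo pairs in which the active duration is longer, with ties as one half.

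- Complete data: 0.5 + 1.5 + 2.5 + 3.5 + 4.5 = 12.5 of 25 pairs, so no difference.
- The active patient with the 96 h fever leaves, febrile, at 12 h, and 12 h is ranked: 0 + 0.5 + 1.5 + 2.5 + 3.5 = 8.0 of 25 pairs (0.32), in favour of active. The longest fever in the arm has become the shortest of all ten.
- The same patient is left out: 0.5 + 1.5 + 2.5 + 3.5 = 8.0 of 20 pairs (0.40). The shift is smaller, but it remains.

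**3. Simulation at two-sided 20%** (the level that matches the SAP's 80% CIs), no true effect. These inputs are assumptions, because the documents give none: exponential fever times with a 3-day median, every patient febrile at the start, loss between 0.5 and 3 days. The arm sizes are Cohort A's 30 per arm (SAP section 3) and Cohort E's 112 per arm (Protocol 6.1). Mann-Whitney is applied to the censoring times as if they were durations.

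| Per arm | Lost | Mann-Whitney rejects |
|---|---|---|
| 30 | 5% v 15% | about 23% |
| 30 | 5% v 25% | about 28% |
| 112 | 5% v 15% | about 28% |
| any | equal | about 20% |

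Log-rank stays at 19-21%. Simulation error is about 1 percentage point.

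**4. A second simulation, one-sided 10%, 30 v 30.** Assumptions: 48 h median, 12-hourly assessments, dropout uniform over the first 72 h, 2,000 runs per row. Patients whose fever ended before they left count as events. The figures are error rates in favour of active under no effect.

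| Dropout, active/placebo | Mann-Whitney on censored times | Mann-Whitney, dropouts excluded | Log-rank | Gehan (generalized Wilcoxon) |
|---|---|---|---|---|
| 20%/20% | 0.10 | 0.10 | 0.10 | 0.10 |
| 10%/5% | 0.12 | 0.11 | 0.10 | 0.10 |
| 20%/5% | 0.18 | 0.14 | 0.10 | 0.09 |
| 30%/5% | 0.29 | 0.21 | 0.11 | 0.11 |
| 5%/20% | 0.05 | 0.07 | 0.11 | 0.11 |

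With a true effect (median 32 v 48 h) and 5%/20% dropout, power is 0.33 for Mann-Whitney on censored times, 0.59 for log-rank and 0.49 for Gehan.

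**The case against.** The strongest reply is that the SAP never says a censoring time is to be ranked. A reader might infer from 5.4.1 and Table 9 that it directs febrile dropouts to be counted as early recoveries. The text does not go that far. Table 9 is titled for time-to-event endpoints, the list in 5.4.2.3 names durations as a separate type, and Kaplan-Meier plots apply only where suitable. Fever could therefore fall outside Table 9, with dropouts simply missing. Or it could count as a time to event, in which case 5.4.1 already permits a suitable test. This stands as a limit on the claim: the misranking is something that could happen. It does not remove the gap. On the first reading fever has no missing-data rule, and exclusion still distorts the test when dropout is unequal, though less. On the second, the word *duration* in the Mann-Whitney sentence points the analyst to the wrong test.

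A reader might also infer that the fever p-value will be biased whatever happens. It will not. With equal loss the error rate stays near nominal, and at 10% versus 5% it moves only from 0.10 to 0.12. Nor is every censored patient misplaced: deaths and patients still febrile at Day 28 take the longest possible time and rank as long.

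The assumed losses are severe for a short illness. Patients who stop study drug continue assessments (SAP Table 4, footnote b), so only withdrawal from the study while febrile counts. Entry requires symptoms of mild or moderate COVID-19, which need not include fever. If fewer patients are febrile, the effective sample is smaller and so is the inflation. All of this stands.

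Finally, the test is optional twice over: formal testing is done only if required, and this particular test is permitted, not mandated. That bears on the importance of the point. It leaves the mismatch in place.

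**Conclusion.** The point holds as a mismatch between SAP 5.4.1 and 5.4.2.3: the test named for duration endpoints cannot use the data as the SAP defines them for the only such endpoint. The harm is conditional. It needs the optional test to be run, dropouts to enter at their Table 9 times (or, to a lesser degree, to be excluded), and febrile dropout to differ between arms. On the stated assumptions, a nominal 20% two-sided test becomes about 23% at Cohort A size with 5% versus 15% lost. It reaches 28% with a wider gap or at Cohort E size, and there is no material inflation under equal loss. These figures illustrate the mechanism and do not predict this trial's error rate. The severity is low: no primary result or design figure depends on it.

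**What to change.** In SAP 5.4.1, delete *and duration* from the Mann-Whitney sentence, and name duration of fever in the sentence on the generalized Wilcoxon and log-rank tests. In SAP 5.4.2.3, state that the Table 9 censoring rules apply to duration of fever. Both edits are needed, since the first alone would leave open whether Table 9 covers fever. The cost is a few words in the SAP. No new method, data or sample size is required, because both replacement tests are already named in that paragraph.

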5.4.2 Secondary Endpoints

5.4.2.1 Secondary Endpoints (Virology)

All secondary virology analyses will be performed on the mITTi population.

All virology analyses will be performed using the nasopharyngeal swab data.

Descriptive analyses of saliva and serum samples will be performed on an exploratory basis for the primary and secondary virology endpoints, as required.

Time to event virology secondary endpoints

For time to event virology secondary endpoints, time will be calculated in hours.

- **Time to cessation of SARS-CoV-2 viral shedding as measured by RT-PCR**
 - Time to cessation of viral shedding by RT-PCR, in hours, is defined as the time between the initiation of any study treatment and first time when a negative or BLQ test result by RT-PCR is obtained. Patients who do not receive a negative or BLQ test result by RT-PCR by the last observation timepoint will be treated as censored at the final timepoint on Day 7.
- **Time to sustained non-detectable SARS-CoV-2 virus RNA**
 - Time to sustained non-detectable SARS-CoV-2 virus RNA, in hours, is defined as the time between the initiation of any study treatment and first time when a negative or BLQ test result by RT-PCR is obtained after which no positive test above or equal to the LOQ was reported. Patients who do not meet this endpoint by the last observation timepoint will be treated as censored at the final timepoint on Day 7.

These time-to-event endpoints will be summarized using descriptive statistics by treatment, as well as Kaplan-Meier plots. The median time to response from the Kaplan-Meier plots will be presented along with the 80% CI. If required, a hazard ratio may be produced adjusting for baseline viral load using a Cox proportional hazards model.

For all cohorts, the virology time-to-event endpoints will be described for the AT-527 group and the pooled placebo group through Day 7 using the mITTi population.

For virology time to event endpoints, deaths will be right censored at Day 7. Consequently, for these endpoints, participants censored on the final day reflect two different states, death or failure to meet the improvement outcome criterion. Therefore, it is important to understand the outcome in the context of the number and timing of deaths by treatment group.

Intercurrent events are those that occur after treatment initiation and either preclude observation of the variable or affect its interpretation. Intercurrent events and missing data will be accounted for through censoring rules, as described in [Table 7](#) below.

Table 7 Virology Time to Event Censoring

Event	Censor	Date and Time
Death prior to meeting endpoint	Yes	Final timepoint on Day 7
Discontinuation or lost to follow-up up to Day 7 for any reason prior to meeting endpoint	Yes	Last observed virology assessment
Do not meet the endpoint	Yes	Final timepoint on Day 7

Proportion virology secondary endpoint

- **Proportion of patients positive for SARS-CoV-2 virus RNA by RT-PCR at specified timepoints**
 - Proportion of patients positive for SARS-CoV-2 virus RNA by RT-PCR will be presented by treatment at each visit. It is defined as the percentage of patients with a positive virus RNA by RT-PCR test result above or equal to the LOQ.

For virology proportion endpoints in all cohorts, the proportion of patients positive for SARS-CoV-2 virus RNA by RT-PCR will be compared between the AT-527 group and the combined placebo group. For all cohorts, the number, proportion and difference in proportions along with 80% CIs will be presented by treatment group for all timepoints.

Missing data will be treated as missing and will not be included in the analysis. However, if a patient dies, the non-responder rule will apply and the patient will be imputed as positive for all timepoints post-death.

Area under the curve (AUC) virology secondary endpoint

- **Area under the curve in the amount of SARS-CoV-2 virus RNA as measured by RT-PCR**
 - AUC in virus RNA (RT-PCR) will be presented by treatment group and is defined as AUC of the amount of virus RNA (RT-PCR). AUC will be calculated using the trapezoidal method. AUC of change from time 0 (t_0) to time K (t_k) is given by the formula:

$$\sum_{k=1}^K \frac{(y_k + y_{k-1})(t_k - t_{k-1})}{2},$$

where t_k (hours) represents the date of the k^{th} virus RNA (RT-PCR) assessment ($k = 0, \dots, K$) and y_k represents the \log_{10} value of the k^{th} virus RNA (RT-PCR) assessment.

For the virology AUC endpoint, the AUC of the amount of virus RNA (RT-PCR) will be compared between the AT-527 group and a combined placebo group. For all cohorts, summary statistics will be presented to Day 7 using the full combined placebo group.

Missing data will be treated as such and not included in the analysis.

If the virus RNA sample has a positive qualitative result, but a quantitative result below the BLQ, virus RNA will be imputed as LOQ – 1 (119 copies/mL). Negative qualitative samples will be imputed as LOQ/2 (60 copies/ml) before being transformed to the log10 scale.

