4.6.2 Patient Discontinuation from the Study

Patients who discontinue from study participation will have an early termination visit 7 (± 2) days after their final dose of study drug. Patients who discontinue from the study after Day 14 will not be required to complete an early termination visit.

Patients have the right to voluntarily withdraw from the study at any time for any reason. In addition, the investigator has the right to withdraw a patient from the study at any time.

Reasons for patient discontinuation from the study may include, but are not limited to, the following:

- Patient withdrawal of consent
- Study termination or site closure
- Adverse event
- Loss to follow-up
- Patient non-compliance, defined as failure to comply with protocol requirements as determined by the investigator or Sponsor

Every effort should be made to obtain a reason for patient discontinuation from the study. The primary reason for discontinuation from the study should be documented on the appropriate eCRF. If a patient requests to be withdrawn from the study, this request must be documented in the source documents and signed by the investigator. Patients who withdraw from the study will not be replaced.

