The rationale for this change is to align the definition of negativity with other external data (e.g., [Fischer et al. 2021](#)) to ensure our findings are comparable and interpretable. Previously, the definition of negativity was based only on the qualitative result determined using cycle threshold (Ct) values. Therefore, a particular viral load threshold was not used; to ensure we have a numeric viral load threshold to define negativity, the limit of quantification (120 copies/mL) is now also considered. Samples that are qualitatively “negative” or quantitatively “BLQ” are now defined to be negative.

Key changes to the SAP, along with the rationale for each change, are summarized below.

Section	Description of Change	Rationale for Change
4	The modified intent-to-treat infected (mITT _i) population definition was updated to ensure that each patient has at least one reverse-transcription polymerase chain reaction (RT-PCR) test result above or equal to the limit of quantification (LOQ)	To align with external data
5.3.5	Additional subgroups of: days from symptom onset to treatment (\leq 3 days, $>$ 3 days); and any underlying health conditions (yes, no) have been added for the primary endpoint	To allow analyses of additional subgroups that may be of interest and/or relevance
5.4.2.1	For the time to cessation of viral shedding and time to sustained non-detectable virus RNA endpoints, receiving a negative result or a result below the limit of quantification (BLQ) now meets the condition for cessation and non-detectability, respectively	To align with external data
5.4.2.1	Updated the censoring date and time for patients that do not meet the time-to-event virology endpoints to the final timepoint on Day 7	To ensure patients remain “at-risk” to assist with the interpretation of the Kaplan-Meier plots at Day 7
5.4.2.1	For the proportion of patients positive endpoint, the definition of positivity was amended to be any RT-PCR test result above or equal to the limit of quantification	To align with external data
5.4.2.3	Modified the censoring date and time for patients that do not meet the efficacy time-to-event endpoints to the final timepoint on Day 28	To align with our handling of other time-to-event endpoints

Additional minor changes have been made throughout to improve clarity and consistency.

TABLE OF CONTENTS

STATISTICAL ANALYSIS PLAN AMENDMENT RATIONALE	3
1. INTRODUCTION	8
1.1 Objectives and Endpoints	9
1.2 Study Design	11

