5. STATISTICAL ANALYSES

5.1 GENERAL CONSIDERATION

All virology and efficacy analyses will be performed on the mITTi population.

All primary and secondary virology endpoints will be produced using the nasopharyngeal swab samples. Additional descriptive analyses for saliva and serum samples will be performed on an exploratory basis for the primary and secondary virology endpoints, as required. A summary of the sampling differences between cohorts is provided in [Table 3](#). Refer to Appendix 1 and Appendix 2 of the study protocol for further details.

No alpha adjustments for multiple comparisons are planned.

For all cohorts, the primary virology analysis will be performed as part of a Day 10 Review (accompanied with key safety review if deemed necessary, see [Section 5.7.1](#)) which is to be completed after all patients enrolled in the current cohort have completed assessments through Day 10. Other endpoints will be analyzed at the completion of each full cohort or at the completion of the study. All analyses at the Day 10 review or at the completion of each cohort will compare each AT-527 dose group and a combined placebo group, including all placebo patients enrolled across cohorts up to the cohort being analyzed, while analyses performed at the completion of the study will compare each AT-527 dose group and a combined placebo group from all cohorts.

Table 3 Differences in Virology Sampling Between Cohorts

Assessment	Cohort A	Cohorts B–E
Nasopharyngeal swab sample for COVID-19 virology	Once a day on Days 1, 3, 5, and 7	Once a day on Days 1, 3, 5, and 7
Saliva sample for COVID-19 virology	NA	Once a day on Days 1, 3, 5, and 7
Serum sample for anti-SARS-CoV-2 antibodies and viral RNA	Once a day on Days 1 and 7	Once a day on Days 1, 3, 5, and 7

COVID-19 = coronavirus disease 2019; NA = not applicable; SARS-CoV-2 = severe acute respiratory syndrome coronavirus-2.

For virology endpoints, the time windows for each assessment are given in [Table 4](#). The time windows will be used for all virology endpoints except the time-to-event endpoints.

Table 4 Virology Assessment Time Windows

Scheduled Timepoint ^{a, b, d}	Acceptable Time Window
Baseline (Day 1 pre-dose)	Day 1 pre-dose ^c
Day 3	Day 2 – Day 3
Day 5	Day 4 – Day 5
Day 7	Day 6 – Day 8

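### Viral-clearance events have no upper time limit while non-clearers are censored at Day 7, so on the literal text a late negative swab can collapse the Kaplan-Meier tail and create a spurious median

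*SAP*

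**What the plan says.** SAP 5.4.2.1 has two time-to-event virology endpoints, both timed in hours from the start of treatment. Cessation of shedding is the "first time when a negative or BLQ test result by RT-PCR is obtained". The sustained endpoint adds that no quantifiable positive follows. Neither definition names a last day on which an event can count.

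The censoring rules are these:
- In the text, patients with no qualifying result "by the last observation timepoint will be treated as censored at the final timepoint on Day 7".
- In Table 7, the row "Do not meet the endpoint" and the row for deaths both censor at the last timepoint on Day 7.
- In Table 7, patients who discontinue or are lost up to Day 7 are censored at "Last observed virology assessment".

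Three further statements bear on the point:
- SAP 5.1: "The time windows will be used for all virology endpoints except the time-to-event endpoints". A swab on Day 8, inside Table 4's Day 6 to Day 8 window for Day 7, therefore keeps its actual time.
- SAP 5.4.2.1: "the virology time-to-event endpoints will be described for the AT-527 group and the pooled placebo group through Day 7 using the mITTi population".
- The SAP amendment rationale says the Day 7 censoring keeps patients at risk "to assist with the interpretation of the Kaplan-Meier plots at Day 7".

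Swabs after Day 7 can occur. Besides a late Day 7 visit and unscheduled visits, Protocol 4.6.2 says: "Patients who discontinue from study participation will have an early termination visit 7" (plus or minus 2) days after the last dose. The schedules in Appendices 1 to 3 mark a nasopharyngeal swab at that visit. After a last dose on Day 5 it falls on Days 10 to 14.

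**The concern.** The Day 7 censoring rule reaches only patients with no negative result by their last observation. A patient first negative on Day 8 does have one, and no row of Table 7 covers that case, so on the literal text the patient is an event on Day 8. A patient still positive on Day 8 is censored a day earlier. Whether someone remains at risk after Day 7 then depends on the result still to come, and the late risk set holds almost only patients about to have the event.

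At stake is the planned headline summary of both endpoints, the Kaplan-Meier plot and the median with its 80% CI. Two programmers could both follow the SAP and report different medians, one of them in a group where most patients never cleared.

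**Working it through.** **Size of group.** The documents give no clearance rate or median for these endpoints. The only figure to reproduce is the group size in SAP Section 3 (one-sided 10% alpha, 80% power):
- Difference 0.7, SD 1.2: n = 2 × (1.2816 + 0.8416)² × (1.2/0.7)² = 26.5, so 27.
- Difference 1.1, SD 1.85: n = 25.5, so 26.
- Inflation: 27/0.9 = 30.

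The stated 27 is reproduced and is used below.

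**Worked example, literal reading.** Assumed: 9 of 27 cleared by Day 7, one first negative at 172 h on Day 8, 17 never cleared, non-clearers censored at 165 h.
- S at Day 7 = 18/27 = 0.667.
- At 172 h one patient is at risk and has the event: S = 0.667 × (1 − 1/1) = 0.
- Reported median 172 h, although 17/27 = 63% never cleared.

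**Varying clearance by Day 7.** n = 27 with one Day 8 negative. Assumed swab times are 48, 96 and 144 h, end of Day 7 at 167 h, and the Day 8 swab at 168 h.

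| Cleared by Day 7 | S at Day 7 | S after Day 8 event (literal) | Median, literal | Median, cut at Day 7 |
|---|---|---|---|---|
| 3 | 0.889 | 0 | 168 h | not reached |
| 5 | 0.815 | 0 | 168 h | not reached |
| 8 | 0.704 | 0 | 168 h | not reached |
| 11 | 0.593 | 0 | 168 h | not reached |
| 16 | 0.407 | 0 | 144 h | 144 h |

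The tail is wrong in every row. The median is wrong only where fewer than half had cleared.

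**Effect of the discontinuation row.** If k discontinued patients are still at risk when one late event occurs, S is multiplied by k/(k + 1). With 5 cleared:
- k = 1: 0.815 × 1/2 = 0.407. The tail does not reach 0, but the median is still 168 h.
- k = 2: 0.815 × 2/3 = 0.543, and no median is reported.

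**How often.** This needs assumptions the documents do not supply. Suppose 20% of patients first clear at the Day 7 visit and 5% or 10% of those visits slip to Day 8. Then p = 0.20 × 0.05 = 0.01, or 0.02, and the chance of at least one late event in a group is 1 − (1 − p)^n. The group sizes are 27, 54 (pooled placebo in Cohorts A to D: (30 + 3 × 10) × 0.9) and 100 (a Cohort E arm).

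Clock time also matters. A Day 8 swab at clock hour v after a first dose at clock hour d falls at 168 + v − d hours. With a dose at 15:00 and a swab at 10:00 that is 163 h. If the Day 7 limit means 168 h after the first dose, the event is late only when v > d. With doses spread evenly over 09:00–20:00 and visits over 09:00–17:00 (assumed), that has probability (8 × 8/2)/(8 × 11) = 0.364, so p becomes 0.0036 or 0.0073.

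| Assumption | Slip | n = 27 | n = 54 | n = 100 |
|---|---|---|---|---|
| Every Day 8 swab falls after the Day 7 limit | 5% | 24% | 42% | 63% |
| Same | 10% | 42% | 66% | 87% |
| Limit 168 h after dose, mixed clock times | 5% | 9% | 18% | 31% |
| Same | 10% | 18% | 33% | 52% |
| Limit 168 h, all doses afternoon and all swabs morning | any | 0% | 0% | 0% |

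These are frequencies of a late event, not of a false median. They ignore discontinued patients still at risk.

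**Candidate remedies on the worked example.**
- Cut events and censoring at the end of Day 7: S = 18/27 = 0.667, median not reached.
- Cut both at the end of Day 8, with non-clearers censored there: 18 at risk, S = 0.667 × 17/18 = 0.630, median not reached.
- Censor non-clearers at their own last swab: if those swabs were on Day 7 (about 148 h), the Day 8 clearer is again alone at risk, so S = 0 and the median is 172 h. This does not work.

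**Cohort E, if the rule were carried over.** Take 100 patients: 25 cleared by Day 7, 10 first negative on Day 14, 65 never. The literal rule has 10 at risk and 10 events, so S goes from 0.75 to 0 with a median at Day 14. With a common Day 14 limit, S = 0.75 × 65/75 = 0.65 and there is no median.

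**The case against.** The strongest reply is that the SAP means follow-up to stop at Day 7. It says the endpoints are described through Day 7, refers to the day of censoring as the final day, and explains the rule by the wish to read the plot at Day 7. On that reading a Day 8 negative is not an event and nothing collapses. This is a fair reading and probably the intention. It stands to the extent that the defect is conditional. It does not remove the point, because the event definition and Table 7 are what a programmer implements, and neither says so.

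A reader might infer more than the documents support:
- That every non-clearer leaves at Day 7. Table 7 makes an exception for patients who discontinue or are lost up to Day 7, and early termination swabs come from patients who discontinue.
- That truncation is also wrong because a Day 8 negative would count as negative at Day 7 in the proportion endpoint but not here. SAP 5.1 states that difference openly. It is a design choice, although aligning the two would be tidier.
- That Day 8 visits are common. Table 4 is an analysis window, and the protocol schedules give a tolerance only for Days 14 and 33. No slip rate is given.
- That group comparisons are badly distorted. A late clearer who is alone at risk across both groups adds nothing to a log-rank statistic or a Cox partial likelihood. The harm is to the curve and the median.

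It is also fair that these are descriptive secondary endpoints in a study the sponsor calls hypothesis-generating, and that the proportion positive at each visit would help a reader spot a spurious tail.

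**Conclusion.** The point holds in a limited form. Followed literally, SAP 5.4.2.1 and Table 7 leave clearance events open-ended while patients who do not meet the endpoint stop at Day 7. One late negative swab then makes the Kaplan-Meier tail drop sharply: to 0 if no discontinued patient is still at risk, or by a factor k/(k + 1) if k are. A median that should be not reached can be reported when fewer than 50% cleared by Day 7. Above that, only the tail is wrong.

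The size within an affected group is large (0.667 to 0 in the example). How often a group is affected cannot be fixed from the documents: from 0% to 87% across the assumptions above. It depends on clearance, visit slip, group size, clock times and what the last timepoint on Day 7 means in hours. The primary endpoint is untouched. The SAP should be corrected, but the trial's main conclusion does not turn on it.

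**What to change.** In SAP 5.4.2.1 and Table 7, state one cut-off for events and censoring, defined in hours or calendar time:
- A first negative or below-quantification result after the cut-off is not an event.
- Patients still in follow-up who have not cleared, and deaths, are censored at the cut-off, not at their own last swab.
- The cut-off is either the end of Day 7, which fits the stated purpose of the amendment, or the end of the Day 7 window (Day 8), which matches the proportion endpoint. The second treats a patient last seen positive on Day 7 as still positive through Day 8.

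When the SAP is updated for Protocol Version 6, apply the same rule at the end of the Day 14 window for Cohort E. The current SAP describes that cohort without a Day 14 swab. If the sponsor quotes a frequency for the artefact, it should be a range with its assumptions.

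The cost is one sentence, a matching edit to Table 7 and a programming rule. No new data are needed.
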